9.1 Adverse events

Information about all adverse events, whether volunteered by the subject, discovered by investigator questioning, or detected through physical examination, laboratory test or other means, will be collected and recorded and followed as appropriate. An adverse event is the appearance or worsening of any undesirable sign, symptom, or medical condition occurring after starting the study drug even if the event is not considered to be related to study drug. Medical conditions/diseases present before starting study drug are only considered adverse events if they worsen after starting study drug. Abnormal laboratory values or test results constitute adverse events only if they induce clinical signs or symptoms, are considered clinically significant, or require therapy. The occurrence of adverse events should be sought by non-directive questioning of the patient at each visit during the study. Adverse events also may be detected when they are volunteered by the patient during or between visits or through physical examination, laboratory test, or other assessments. As far as possible, each adverse event should be evaluated to determine:

- The severity grade (grade 1-4, or mild/moderate/severe)
- Its relationship to the study drug(s) (suspected/not suspected)
- Its duration (start and end dates or if continuing at final exam)
- Action taken (no action taken; study drug dosage adjusted/temporarily interrupted; study drug permanently discontinued due to this adverse event; concomitant medication taken; non-drug therapy given; hospitalization/prolonged hospitalization)
- Whether it constitutes a serious adverse event (SAE)

All adverse events should be treated appropriately. Such treatment may include changes in study drug treatment including possible interruption or discontinuation, starting or stopping concomitant treatments, changes in the frequency or nature of assessments, hospitalization, or any other medically required intervention. Once an adverse event is detected, it should be followed until its resolution, and assessment should be made at each visit (or more frequently, if necessary) of any changes in severity, the suspected relationship to the study drug, the interventions required to treat it, and the outcome.

Information about common side effects already known about the investigational drug can be found in the Investigator's Brochure or will be communicated between Investigator Brochure updates in the form of Investigator Notifications. This information will be included in the patient informed consent and should be discussed with the patient during the study as needed.

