6.2.1.1 Definitions

Definition of adverse event (AE)

In a clinical study, an AE is any untoward medical occurrence (i.e. any unfavorable and unintended sign [including abnormal laboratory findings], symptom or disease) in a patient or clinical investigation subject after providing written informed consent for participation in the study. Therefore, an AE may or may not be temporally or causally associated with the use of a medicinal (investigational) product.

A surgical procedure that was planned prior to the start of the study by any physician treating the subject should not be recorded as AE (however, the condition for which the surgery is-required may be an AE if worsens compared to baseline).

- Conditions that started before signing of informed consent and for which no symptoms or treatment are present until signing of informed consent are recorded as medical history (e.g. seasonal allergy without acute complaints).
- Conditions that started before signing of informed consent and for which symptoms or treatment are present after signing of informed consent, at *unchanged intensity*, are recorded as medical history (e.g. allergic pollinosis).
- Conditions that started or deteriorated after signing of informed consent will be documented as adverse events.

Definition of serious adverse event (SAE)

An SAE is classified as any untoward medical occurrence that, at any dose, meets any of the following criteria (a – f):

- a. Results in death.
- b. Is life-threatening.

The term 'life-threatening' in the definition refers to an event in which the patient was at risk of death at the time of the event, it does not refer to an event which hypothetically might have caused death if it were more severe.

- c. Requires inpatient hospitalization or prolongation of existing hospitalization.

A hospitalization or prolongation of hospitalization will not be regarded as an SAE if at least one of the following exceptions is met:

- The admission results in a hospital stay of less than 12 hours.
- The admission is pre-planned.
(i.e. elective or scheduled surgery arranged prior to the start of the study)
- The admission is not associated with an AE.
(e.g. social hospitalization for purposes of respite care).

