6.2.1.2.2 Intensity

The intensity of the AE is classified according to the CTCAEv4.0. Grade refers to the severity (intensity) of the AE:

CTCAEv4 Grade 1: mild; asymptomatic or mild symptoms; clinical or diagnostic observations only; intervention is not indicated.

CTCAEv4 Grade 2: moderate; minimal, local, or noninvasive intervention is indicated; limiting to age-appropriate instrumental activities of daily living (ADL; instrumental ADL refers to preparing meals, shopping for groceries or clothes, using the telephone, managing money, etc).

CTCAEv4 Grade 3: Severe or medically significant but not immediately life threatening; hospitalization or prolongation of hospitalization is indicated; disabling;

limiting to self care ADL (self care ADL refers to bathing, dressing and undressing, feeding self, using the toilet, taking medications, and not bedridden).

CTCAEv4 Grade 4: life-threatening consequences; urgent intervention is indicated.

CTCAEv4 Grade 5: death due to an AE.

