9.2 Serious adverse events

A serious adverse event is an undesirable sign, symptom or medical condition which:

- is fatal or life-threatening
- results in persistent or significant disability/incapacity
- constitutes a congenital anomaly/birth defect
- requires inpatient hospitalization or prolongation of existing hospitalization, unless hospitalization is for routine treatment or monitoring of the studied indication
- is medically significant, i.e., defined as an event that jeopardizes the patient or may require medical or surgical intervention to prevent one of the outcomes listed above

Information about all serious adverse events will be collected and recorded. To ensure patient safety, each serious adverse event must be reported to the PI and to Bayer expeditiously. Moffitt Cancer Center and all participating sites will report SAEs by completing an SAE report in ONCORE, the electronic data capture system and a Medwatch Form online at <http://www.fda.gov/medwatch> The SAE must be reported by email ([contact]) to the MCRN within 2 working days.

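### Sections 6.2.1.1 and 9.1 define an adverse event differently (start point and laboratory rule), and Section 8.2 does not say which definition the secondary safety endpoint uses

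*Combined protocol and SAP*

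**What the plan says.** **Section 6.2.1.1 (Definitions)** takes an adverse event to be "any unfavorable and unintended sign [including abnormal laboratory findings], symptom or disease" arising once consent has been given. Its recording rule is explicit: "Conditions that started or deteriorated after signing of informed consent will be documented as adverse events". It states no filter for clinical significance.

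**Section 9.1 (Adverse events)** requires the event to be one "occurring after starting the study drug even if the event is not considered to be related to study drug". A condition already present at first dose counts only if it then worsens. On laboratory results it is restrictive: "Abnormal laboratory values or test results constitute adverse events only if they induce clinical signs or symptoms", or if they are thought clinically important or call for treatment.

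**Section 8.2 (Statistical Analysis)** lists toxicity as a secondary endpoint and promises a descriptive summary of adverse event frequency and severity. It cites neither section and fixes no event window or laboratory criterion.

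**Section 6.2 (Safety)** makes everyone who took any study drug valid for the safety analysis. It also lists laboratory changes as a safety variable alongside adverse events.

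**The concern.** The frequency and severity of adverse events is the first secondary objective, in both the synopsis and Section 2. A frequency needs a rule for what counts as an event, and here there are two, with no statement of precedence. An analyst working from Section 8.2 cannot tell which table is meant.

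The laboratory rule is the part that matters most. Section 4.1.1 admits patients with bilirubin up to 2.0 times the upper limit of normal, transaminases up to 5 times that limit when the liver is involved, and platelets from 75,000. The calendar in Section 6.1 schedules blood counts and chemistry every two weeks in cycles 1 and 2. Changes in laboratory values without symptoms are therefore to be expected, and whether each is an adverse event depends on the section applied. An abnormality left out under Section 9.1 would be missing from the adverse event tables. Section 8.1 expects 6-7 institutions, so the choice would be made in several places.

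**Working it through.** The documents give no expected adverse event rate, precision or threshold, so there is no planned figure to reproduce. The check is a comparison of the texts.

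**Step 1: classify the same event under each rule.**

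| Event in a treated patient | Section 6.2.1.1 | Section 9.1 |
|---|---|---|
| New symptom after first dose | counted | counted |
| New symptom after consent that does not worsen after first dose | counted | not counted |
| New unfavourable laboratory abnormality after first dose, without symptoms, not judged important, untreated | counted | not counted |
| The same abnormality, judged clinically important | counted | counted |
| Condition present before consent, unchanged | not counted (medical history) | not counted |

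Consent precedes first dose, so every event that meets Section 9.1 also meets Section 6.2.1.1. The Section 9.1 set lies inside the other. The two differ in exactly two groups: events between consent and first dose, and laboratory abnormalities that fail the Section 9.1 filter.

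**Step 2: how long the first gap can be.** Section 6.1 places informed consent in the pre-study column and allows required studies within 28 days before treatment. That is as long as one 28-day cycle. No maximum interval from consent to first dose is stated.

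**Step 3: look for a rule that settles it.**
- Section 8.2 names no definition.
- Section 6.2 fixes which patients are analysed, not which of their events. Treated patients can have events before first dose.
- Section 9.3 points to Section 6.2.1.1, but only for serious adverse events.

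None of these decides the adverse event definition.

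**Step 4: size, on assumed shares only.** Let w be the share of Section 6.2.1.1 events that fall before first dose, and l the share of the remainder that are laboratory findings failing the Section 9.1 filter. The ratio of event counts, Section 6.2.1.1 to Section 9.1, is 1 / ((1 - w)(1 - l)).
- w = 0, l = 0: ratio 1.00.
- w = 0.05, l = 0.30: 1 / (0.95 × 0.70) = 1.50.
- w = 0.20, l = 0.50: 1 / (0.80 × 0.50) = 2.50.

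The documents give neither w nor l. The range 1.00 to 2.50 shows how the ratio behaves under these assumptions and is not an estimate for this trial.

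**The case against.** The strongest reply is that the definitions are nested and the data allow a repair. Sections 6.2 and 9.1 both call for start dates, so events before first dose can be separated. The safety population is treated patients, and the causality guidance in Section 6.2.1.2.3 expects a related event to follow the drug. Section 6.2 also keeps laboratory changes as a variable in their own right and requires all pertinent safety observations to be reported.

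Much of this stands for the start point. A reader might infer that events before first dose will be tabulated as regimen toxicity, but the documents do not say so and dates allow the split. Two gaps remain. A filter on start date alone would miss a condition that began before first dose and worsened afterwards. And separate reporting of laboratory changes does not restore to the adverse event tables an abnormality that was never recorded as an event.

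Several stronger readings are not supported:
- **Every abnormal laboratory value is an event under Section 6.2.1.1.** The text requires the finding to be unfavourable and unintended. What it lacks is a significance filter.
- **Fatal events have no grade.** Section 9.1 does say "The severity grade (grade 1-4, or mild/moderate/severe", but Section 6.2 and the opening of Section 9 adopt CTCAE v4.0 for the trial, and Section 6.2.1.2.2 includes "CTCAEv4 Grade 5: death due to an AE". This is loose wording.
- **There are two competing definitions of a serious event.** The hospital exemptions differ: Section 6.2.1.1 has "The admission results in a hospital stay of less than 12 hours", and Section 9.2 has "unless hospitalization is for routine treatment or monitoring of the studied indication". But Section 9.3 names Section 6.2.1.1 as the definition.
- **Each reclassified patient moves an incidence by 1/39 = 2.6 points.** The 39 are patients evaluable for survival, with replacement under Sections 4.2.3 and 8.1. The safety denominator is all treated patients and can exceed 39, so in a completed trial 2.6 points is a ceiling.
- **Two-weekly tests throughout will shift many patients.** The calendar shows that frequency for cycles 1 and 2 and one draw in cycle 3. No count of patients follows.
- **Sites will in fact diverge.** Section 11.4 describes one data system with monitoring, and the case report form instructions are not in these documents. Divergence is a risk, not an established fact.

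**Conclusion.** The point holds for the start point and the laboratory rule. Two operative definitions give different adverse event counts from the same patients, and Section 8.2 does not choose between them. The laboratory rule is the more consequential of the two, because start dates can largely deal with the other.

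The size of the shift cannot be derived from the documents. The effect is confined to a descriptive secondary endpoint with no test or threshold attached. The primary decision, at least 16 of 39 evaluable patients alive at 6 months, uses no adverse event data, so its error rate, power and sample size are untouched. The change should be made, but the trial's main conclusion does not depend on it. The verdict assumes that no instruction outside these documents already settles the definition.

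**What to change.** 1. Keep one adverse event definition in Section 6.2.1.1, with an explicit start point and laboratory criterion, and have Section 9.1 refer to it.
2. State in Section 8.2 that the safety tables cover every patient who took study drug and count events that start or worsen from first dose, with events between consent and first dose listed separately.
3. State in Section 8.2 that laboratory toxicity is tabulated by CTCAE v4.0 grade from the measured values, so that it does not depend on which rule a site applied.
4. As tidying only, bring the severity wording in Section 9.1 into line with the CTCAE v4.0 grades 1-5 already adopted, and the serious event wording in Section 9.2 into line with Section 6.2.1.1.

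The cost is protocol wording and one table specification. The laboratory values and event dates are already to be collected, so no new data and no change to the sample size are needed.

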9.2 Serious adverse events

A serious adverse event is an undesirable sign, symptom or medical condition which:

- is fatal or life-threatening
- results in persistent or significant disability/incapacity
- constitutes a congenital anomaly/birth defect
- requires inpatient hospitalization or prolongation of existing hospitalization, unless hospitalization is for routine treatment or monitoring of the studied indication
- is medically significant, i.e., defined as an event that jeopardizes the patient or may require medical or surgical intervention to prevent one of the outcomes listed above

Information about all serious adverse events will be collected and recorded. To ensure patient safety, each serious adverse event must be reported to the PI and to Bayer expeditiously. Moffitt Cancer Center and all participating sites will report SAEs by completing an SAE report in ONCORE, the electronic data capture system and a Medwatch Form online at <http://www.fda.gov/medwatch> The SAE must be reported by email ([contact]) to the MCRN within 2 working days.

9.3 Reporting of serious adverse events

The definition of serious adverse events (SAEs) is given in Section 6.2.1.1.

Each serious adverse event must be followed up until resolution or stabilization, by submission of updated reports to the designated person. An isolated laboratory abnormality that is assigned grade 4, according to CTC definition, is not reportable as an SAE; unless the investigator assesses that the event meets standard ICH criteria for an SAE. CTC grade 4 baseline laboratory abnormalities that are part of the disease profile should not be reported as an SAE, specifically when they are allowed or not excluded by the protocol inclusion/exclusion criteria.

When required, and according to local law and regulations, serious adverse events must be reported to the Ethics Committee and Regulatory Authorities.

All serious adverse events should be reported to Bayer within 24 hours. In the event of such an event, the investigator should refer to the Pharmacovigilance section of the contract for reporting procedures.

The Investigator may report serious adverse events (SAEs) as described below.

A MedWatch form available at <http://www.fda.gov/medwatch/>

All reports shall be sent electronically to:

Electronic Mailbox: [contact]

[contact]

Address: Global Pharmacovigilance - USA
Mail only: Bayer HealthCare Pharmaceuticals Inc.

[name]
[name]

Address: [name]
FDX or UPS only [name]

Reports for all Bayer products can also be phoned in via our Clinical Communications Dept:

[contact]

9.4 Adverse events of special safety interest

As with any new chemical entity, there is always potential for unexpected adverse events, including hypersensitivity reactions.

Based on data from phase I/II studies with regorafenib and from current knowledge of the pharmacological properties of other small molecule tyrosine kinase inhibitors in this drug class, as soon as there is reasonable suspicion of any of the following AEs, the investigator should immediately notify the sponsor as outlined in Section 7.6.1.4.

These events are:

- Acute renal failure (NCI-CTCAE version 4.0 \geq grade 3) or severe proteinuria (NCI-CTCAE version 4.0 \geq grade 3)
- Interstitial lung disease
- Acute cardiac failure
- Clinically significant bleeding (NCI-CTCAE version 4.0 \geq grade 3)
- Stevens-Johnson Syndrome and erythema multiforme
- Hepatic failure

9.5 Pregnancies

The investigator must report to Bayer any pregnancy occurring in a study subject, or in his partner, during the subject's participation in this study. The report should be submitted within the same timelines as an SAE, although a pregnancy per se is not considered an SAE.

For a study subject, the outcome of the pregnancy should be followed up carefully, and any abnormal outcome of the mother or the child should be reported.

For the pregnancy of a study subject's partner, all efforts should be made to obtain similar information on course and outcome, subject to the partner's consent.

For all reports, the forms provided are to be used.

9.6 Further safety

Progressive disease

If progressive disease leads to signs and symptoms that meet the criteria for an SAE (i.e., hospitalization, disability, death, or important medical event), the signs and symptoms should be reported as an SAE and not the underlying progressive disease.

Death

If any subject dies during the trial or within 30 days of the end-of-treatment visit, the investigator will inform Bayer and record the cause of death in detail (using the SAE Form) within 24 hours.

10. Premature termination of the study

- If risk-benefit ratio becomes unacceptable owing to, for example,
 - Safety findings from this study (e.g. SAEs)
 - Results of any interim analysis
 - Results of parallel clinical studies
 - Results of parallel animal studies (on e.g. toxicity, teratogenicity, carcinogenicity or reproduction toxicity).
- If the study conduct (e.g. recruitment rate; drop-out rate; data quality; protocol compliance) does not suggest a proper completion of the trial within a reasonable time frame.

The investigator has the right to close his/her center at any time.

For any of the above closures, the following applies:

- Closures should occur only after consultation between involved parties.
- All affected institutions (e.g. IEC(s)/IRB(s); competent authority (ies); study center; head of study center) must be informed as applicable according to local law.
- In case of a partial study closure, ongoing subjects, including those in post study follow-up, must be taken care of in an ethical manner.

Details for individual subject's withdrawal can be found in Section 4.2.1.

11. Data recording

11.1 Institutional Review Board (IRB) Approval and Consent

It is expected that the IRB will have the proper representation and function in accordance with federally mandated regulations. The IRB should approve the consent form and protocol.

In obtaining and documenting informed consent, the investigator should comply with the applicable regulatory requirement(s), and should adhere to Good Clinical Practice (GCP) and to ethical principles that have their origin in the Declaration of Helsinki.

Before recruitment and enrollment onto this study, the patient will be given a full explanation of the study and will be given the opportunity to review the consent form. Each consent form must include all the relevant elements currently required by the FDA Regulations and local or state regulations. Once this essential information has been provided to the patient and the investigator is assured that the patient understands the implications of participating in the study, the patient will be asked to give consent to participate in the study by signing an IRB-approved consent form.

11.2 Required Documentation

Before the study can be initiated at any site, the site will be required to provide regulatory documentation to the Moffitt Clinical Research Network (MCRN) at Moffitt Cancer Center.

Sites must provide a copy of their informed consent to the MCRN coordinating center for review and approval prior to submission of any documents to the site's IRB. Any changes requested by the site's IRB must be provided to the MCRN staff for review and approval prior to resubmission to the IRB.

The MCRN Coordinating Center must receive the following trial specific documents either by hardcopy, fax, or email before a site can be activated for any trial:

1. IRB Approval Letter that includes the protocol version and date
2. FDA Related Forms 1572/1571/310 as appropriate
3. Signed Protocol Title Page
4. IRB Approved Consent Form
5. Site Delegation of Responsibility Log
6. Signed Financial Interest Disclosure Forms (principal and sub investigators)
7. Updated Investigator/Personnel documents (CVs, licenses, Conflict of Interest statements, etc) as needed
8. Updated Laboratory Documents (certifications, normal ranges, etc) as needed Signed protocol specific Task Order

A study initiation visit (or teleconference) will be held prior to the start of any study related activity at the site. Attendance is required for:

- The site PI and appropriate research staff
- Moffitt PI and MCRN research coordinator is required

The requirements of the protocol and all associated procedures and processes will be reviewed and agreed upon prior to the activation of the study. The MCRN utilizes the EDC system, OnCore. OnCore training will be scheduled if indicated with the appropriate staff from the site.

